## Hypothesis

- List the clinical Hypotheses in order of priority:

**Hypothesis 1:** Hyperaroused PI sufferers will show greater performance deficits (slower reaction times; fewer correct responses and more error responses) across repeated daytime testing trials than will age- and gender-matched normal sleepers.

**Hypothesis 2:** Complex reaction time tasks that require executive function, ability to switch attention, and higher order memory function will show greater discrimination of hyperaroused PI sufferers and normal sleepers on measures of mean reaction time, correct response rates and error rates than will simple reaction time tasks.

**Exploratory Aim 3:** To determine the possible sleep deficiencies/mechanisms that contribute to the relative daytime deficits in the hyperaroused PI subgroups we will test measures of sleep continuity (sleep and wake time) and the macro-architecture (sleep stage percentages) and micro-architecture (NREM sleep EEG spectral measures) derived from PSG on nights preceding daytime testing as covariates in study analyses to determine the degree to which they account for observed group differences.

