Following each administration of the performance testing, the participant will be placed in a laboratory bedroom for the MSLT trial. Most aspects of the standard protocol will be followed in conducting the MSLT. However, conservative MSLT criteria rather than contemporary clinical criteria will be used to define the sleep latency for each nap. Specifically, sleep latency will be defined as the time between the beginning of the nap trial and either the first three consecutive 30-second epochs of stage 1 sleep or the first 30-second epoch of any other sleep stage. If no sleep occurs, the trial will end at 20 minutes and a sleep latency of 20 minutes will be assigned. To minimize carry-over effects from one nap to the next, each nap trial will be discontinued 5 minutes after the sleep onset criterion is met.

Once all participants have completed the study protocol we will compare our groups of PI and NS in regard to their mean sleep onset latencies shown on the four MSLT naps to assure the groups do not differ in regard to their observed levels of daytime alertness. The dependent measures we plan to use in study analyses include: (1) mean reaction time per trial for each test; (2) # of correct responses per trial for each test; (3) # of errors of commission per trial for each test; (4) # of errors of omission per trial for each test; and (5) total # of errors per trial for each test. Our analysis plan below outlines how these measures will be used to test our study aims and hypotheses.

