## Statistical Plans

- Include justification for clinical sample size and primary hypothesis testing:

As noted above, our main dependent variables of interest will include: (1) mean reaction time per trial for each test; (2) # of correct responses per trial for each test; (3) # of errors of commission per trial for each test; (4) # of errors of omission per trial for each test; and (5) total # of errors per trial for each test. We will use these data to test Hypotheses 1-2 and to address our exploratory Aim which will examine the relationship between various nocturnal sleep measures and daytime performance scores. Our hypotheses testing will be accomplished using a 2 (PI vs. NS) x 2 (simple vs. complex test)

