# A

factorial analysis. Although our statistical model could also include "trials" as a factor, we have chosen to limit the complexity of our analyses by excluding this factor and using mean values of each of our performance measures across trials for each participant in our analyses. To further simplify our analyses we will compute mean values of our 5 dependent measures for the three simple tests and another set of mean values of these dependent measures for our three complex tests and use those composite means in all planned analyses.

Before conducting tests of the study hypotheses, we will conduct a number of preliminary 2 (PI vs. NS) x 2 (alert vs. sleepy) x 2 (simple vs. complex test) ANOVAs and cross tabs analyses to determine if the various "cells" of our study include participants who do not differ significantly in terms of their mean ages, years of education, gender compositions and racial/ethnic compositions. If study "cells" are found to differ significantly on any of these variables, those variables will be used as covariates in statistical models designed to test study hypotheses. If study cells do not differ in regard to these variables we will use unadjusted statistical models to test study hypotheses.

For study hypotheses 1 & 2, we will conduct 2 (PI vs. NS) x 2 (simple vs. complex test) MANOVAs/MANCOVAs analyses to test for statistical significance across the multiple performance measures derived from the neuro-cognitive test battery. If the MANCOVA/MANOVA shows significant results, univariate ANCOVAs/ANOVAs will be conducted to tests for similar significant effects for each individual performance measure (i.e., mean reaction time; within subject standard deviations for reaction time; error responses).

Hypothesis 1 will be tested via examination of the main effect of the *group factor* (PI vs. NS) in these analyses. Findings showing significantly slower and more variable reaction times, fewer correct responses and higher error rates in the hyperaroused PI group will support this hypothesis. Elimination of these statistical differences in repeat analyses that use hyperarousal scale scores as a covariate will confirm the role of hyperarousal in explaining the observed group differences.

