Hypothesis 2 will be tested via examination of the interaction of the *group factor* (PI vs. NS) and *test difficulty factor* (simple vs. complex) in these analyses. This finding coupled with a posteriori comparisons showing that PI participants have significantly poorer performances than do NS only on the complex tasks will support this hypothesis. Again, elimination of these statistical differences in repeat analyses that use each participant's hyperarousal scale score as a covariate will confirm the role of hyperarousal in explaining the observed group differences on complex tasks.

Our Exploratory Aim will require us to derive a variety of measures from the PSGs conducted on the two nights preceding daytime testing. Following the AASM Scoring Manual guidelines we will score these PSG records and obtain measures of total sleep time, sleep onset latency, wake time after sleep onset, sleep efficiency, and percentages of stages N1, N2, N3, and R for each night. We also will de-artifact each night and then perform a Fast Fourier Transform and subsequent sleep EEG spectral analysis as per our previously published reports to derive NREM absolute and relative spectral power measures in the delta, theta, alpha, sigma, beta and gamma bandwidths. Once these measures are derived for each night, we will compute mean values of these measures for the two PSG nights and then enter those into multivariate regression analyses to determine which measures predict each of the five performance variables used as dependent measures. Those found to be predictive of performance indices will be entered as covariates in the above factorial analyses to determine if any such measures account for the anticipated relative deficits shown by the insomnia group vis a vis the normal group. Since we will anticipate group differences only on the 5 performance measures derived from the set of complex tests, we will plan to test our sleep measures as covariates only in one-way group comparisons using response latency, correct response rate, and error rate data acquired from the complex tests as dependent measures in these analyses. We, thus, will conduct and 5 ANCOVA analyses in which the sleep measures are tested as covariates with each of the 5 performance measures obtained from the complex reaction time tests.

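### The demographic check compares simple/complex cells that hold the same people, and the outcome lists for the MANOVA, its follow-up tests and the Hypothesis 1 criterion do not agree

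*Combined protocol and SAP*

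**What the plan says.** All references are to the combined protocol and SAP.

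**Outcomes.** Study Design/Clinical Plan sets out five measures, beginning "The dependent measures we plan to use in study analyses include: (1) mean reaction time per trial for each test". Statistical Plans repeats the list and ends it with "4) # of errors of omission per trial for each test; and (5) total # of errors per trial for each test". The five are mean reaction time (RT), correct responses, commission errors, omission errors and total errors. Statistical Plans will then "compute mean values of our 5 dependent measures for the three simple tests and another set of mean values" for the three complex tests, and will "use those composite means in all planned analyses". The Exploratory Aim again counts five, with ANCOVAs on "each of the 5 performance measures obtained from the complex reaction time tests".

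The MANOVA for Hypotheses 1 and 2 is described only as covering the multiple performance measures from the battery. If it is significant, univariate tests follow for "each individual performance measure (i.e., mean reaction time; within subject standard deviations for reaction time; error responses". Support for Hypothesis 1 is described as "Findings showing significantly slower and more variable reaction times, fewer correct responses and higher error rates" in the insomnia (PI) group. The Hypothesis section itself names "slower reaction times; fewer correct responses and more error responses", with no mention of variability.

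**Demographic check.** Before the hypothesis tests, Statistical Plans runs ANOVAs and cross tabs in a 2 (PI or normal sleeper, NS) x 2 (alert or sleepy) x 2 (simple or complex test) layout. These compare age, education, gender and race/ethnicity across cells. A variable that differs becomes a covariate in the hypothesis models; otherwise those models are unadjusted. Study Design/Clinical Plan gives every participant both the simple and the complex tests, in alternating order.

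**The concern.** Age, education, gender and race/ethnicity belong to the person. Crossing them with a factor that every person occupies at both levels compares people with themselves. The difficulty terms can show nothing. If the rows are entered as separate observations, the remaining terms are tested on twice the real sample. The check matters because it chooses between adjusted and unadjusted hypothesis models. It also shows that the plan has not stated that difficulty is a repeated factor, and Hypothesis 2 rests on the group-by-difficulty interaction.

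For the outcomes, the plan gives three different lists where one is needed. An analyst cannot tell from the text whether RT variability is inside the MANOVA that gates the univariate tests, or whether correct responses are to be followed up. Left open, that choice could be made after the data are seen. The undefined total-error count adds a technical problem to the same MANOVA.

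**Working it through.** **1. The plan's own figures.** Inputs from Power Considerations: 82 per group and alpha .05 (taken as two-sided, which reproduces). Power ≈ Φ(δ / (σ√(2/82)) − 1.96), with √(2/82) = 0.1562.

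| Measure | δ/σ | δ/(σ × 0.1562) | Power | Stated |
|---|---|---|---|---|
| Errors | 1.86/3.45 | 3.45 | .932 | .93 |
| Correct responses | 1.8/3.74 | 3.08 | .869 | .87 |
| RT | 49.8/112.1 | 2.84 | .812 | .81 |
| Complex latency | 58.51/133.4 | 2.81 | .802 | .80 |
| Simple latency | 21.5/66.8 | 2.06 | .540 | .54 |

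All reproduce and none is challenged. No power is given for RT variability.

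**2. Demographic check.** Each of the 164 people contributes one value per variable, which appears under both simple and complex: 328 rows.

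- *Effects involving difficulty.* Simple and complex means are identical in every group-by-alertness cell. The sums of squares for difficulty and its three interactions are therefore zero for any data: 4 of 7 effects.
- *The other three (group, alertness, group x alertness), rows stacked and treated as independent.* Effect and error sums of squares both double. Error df go from 164 − 4 = 160 to 328 − 8 = 320. So F(stacked) = F(per person) × 320/160 = 2 × F(per person). The 5% critical value F(1,320) is 3.871, so the real rate is P(F(1,160) > 3.871/2 = 1.935) = .166. Simulation (20,000 runs, assumed sleepy shares of 10, 25 and 40%) gave .163 to .169, against .049 to .052 with one row per person.
- *Omnibus tests over four cells (group x difficulty, 3 df).* ANOVA: P(F(1,162) > 1.5 × 2.632 = 3.949) = .049. Cross tab of a two-category variable: P(χ² on 1 df > 7.815/2 = 3.907) = .048.
- *Omnibus tests over all eight cells (7 df).* ANOVA: P(F(3,160) > (7/6) × 2.038 = 2.378) = .072. Cross tab: P(χ² on 3 df > 14.067/2 = 7.034) = .071.

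Age and gender are matched by design, so this mainly concerns education and race/ethnicity.

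**3. Outcome lists side by side.**

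| Place | Mean RT | RT variability | Correct | Errors |
|---|---|---|---|---|
| Five-measure list | yes | no | yes | commission, omission, total |
| Univariate follow-up | yes | yes | no | yes, not split |
| Hypothesis 1 criterion | yes | yes | yes | yes, not split |
| Hypothesis section | yes | no | yes | yes, not split |

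Only mean RT and errors in some form are in every row. RT variability is supplied by the battery (Study Design/Clinical Plan), so no data are missing.

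**4. Total errors.** Assume total = omission + commission. Then omission + commission − total = 0 for everyone, and the five-measure covariance matrix has rank 4. Any four measures that keep two of the three error counts carry the same information. In simulated data Wilks' lambda was .98513 whether total, omission or commission was dropped.

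**5. Cost of adding RT variability to the MANOVA.** Hotelling T² for two groups, N = 164, p measures: F on p and 164 − p − 1 df. The worst case is that variability adds no group separation, because adding a measure cannot reduce the Mahalanobis distance. The noncentrality is held fixed.

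| Measures | Power before | Power after |
|---|---|---|
| 4 to 5 | .80 | .764 |
| 4 to 5 | .90 | .875 |
| 3 to 4 | .80 | .755 |
| 3 to 4 | .90 | .869 |

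**The case against.** The strongest reply is that these are drafting faults with no demonstrated effect on a conclusion. Much of it stands.

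- *A reader might infer that the Hypothesis 1 criterion cannot be carried out.* It can: the follow-up list names a univariate test of within-subject RT standard deviation, and the battery supplies the measure.
- *A reader might infer that RT variability is definitely outside the MANOVA.* The MANOVA outcomes are not itemised. Its exclusion follows from the five-measure list together with the statement that those composites serve all planned analyses. That is the better-supported reading, but it is an inference.
- *The absence of correct responses from the follow-up list may be shorthand.* Agreed; they are in the Hypothesis 1 criterion, and this carries little weight.
- *A reader might infer that the .166 rate carries over to Hypothesis 1 or 2.* It does not. It is the rate at which a check on covariates flags a difference, and only if rows are stacked and tested on 1 df, which the plan neither says nor rules out. The usual consequence is an extra covariate.
- *A reader might infer that singularity invalidates the omnibus test.* It depends on a definition the plan does not give, and dropping any one error count leaves the result unchanged.
- *The text already shows that difficulty is within-person.* It shows that everyone takes both tests, but it never says that the analysis will respect this, and the demographic check treats the two levels as separate cells.

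What the reply does not answer is that the check, as specified, contains a factor that cannot inform it, and that the outcome lists disagree within a single section.

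**Conclusion.** The point holds and should be fixed.

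The demographic check is wrong as specified: four of seven effects are zero by construction. The other three have a false-positive rate of .166 if 328 rows are treated as independent; with one row per person the rate is nominal. Omnibus cell tests run at .048 to .072. No effect on the type I error or power of Hypothesis 1 or 2 is claimed. The consequence of ignoring the pairing in the Hypothesis 2 interaction is not sized, because it depends on the simple–complex correlation, which the documents do not give.

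The outcome lists conflict over RT variability. The criterion is executable, but on the all-planned-analyses reading one of its components lies outside the MANOVA that gates it. Rank 4 of 5 rests on total errors being the sum of the two error types, and it leaves the omnibus result unaffected once one count is removed.

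**What to change.** 1. Compare demographics between PI and NS only, one row per person. This also removes the alert/sleepy factor, which is not in the 2 x 2 hypothesis model.
2. State that test difficulty is a within-participant factor: test Hypothesis 1 on each person's average over difficulty, and Hypothesis 2 on each person's complex-minus-simple difference.
3. Use one outcome list for the MANOVA, the follow-up tests and the Hypothesis 1 criterion, and say explicitly that correct responses are followed up. For RT variability, choose one of two routes. Either add it to the list, averaged over trials and tests like the others, or remove it from the Hypothesis 1 criterion and label it secondary.
4. Define total errors, and test it only univariately, behind the same gate. If the test definitions also make correct responses an exact complement of errors in every test averaged, take them out of the multivariate model too and keep their univariate test.

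The cost is wording only: no new data and no change in sample size. Adding RT variability may lower omnibus power by at most about .04 to .045 from .80. Making it secondary avoids that, but removes it from the evidence for Hypothesis 1.

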## Study Design/Clinical Plan

- Provide a concise overview stating the type of experimental design

This study will use a matched-groups cross-sectional experimental design. Age and gender matched groups of hyperaroused PI sufferers and non-complaining normal sleepers (NS) will be recruited and enrolled. A comprehensive screening process that includes structured sleep and psychiatric interviews, screening questionnaires, vitals, urine pregnancy test, medical history, and diagnostic PSG will be used to determine eligible subjects. Our screening procedures and selection criteria are designed to allow us to identify and enroll hyperaroused PI sufferers and normally alert normal sleepers. PI sufferers enrolled will meet Research Diagnostic Criteria for insomnia disorder, score  $> 14$  on the Insomnia Severity Index, report insomnia for  $> 3$  months, have sleep difficulties  $\geq 3$  nights per week, score  $\leq 3$  on the Epworth Sleepiness Scale (ESS), score  $\geq 29$  on the Hyperarousal Scale and report an inability to nap in the daytime. The normal sleepers enrolled will report general satisfaction with sleep and no sleep/wake complaints, score  $\leq 10$  on the ESS, score  $< 25$  on the Hyperarousal Scale, and deny a practice of routine daytime napping. Those excluded will have: (a) a sleep-disruptive medical condition (e.g., rheumatoid arthritis); (b) a current major psychiatric (Axis I) condition on the basis of a Structured Clinical Interview for Psychiatric Disorders (SCID); (c) sedative hypnotic dependence and unwillingness/inability to abstain from these medications while in the study; (d) use of anxiolytics, antidepressants, or any other psychotropic medication; or (e) an apnea/hypopnea index (AHI)  $> 5$  or a periodic limb movement-related arousal index  $> 15$  during on screening PSG that includes a full sleep montage to allow for detection/diagnosis of sleep-disordered breathing and PLMD. Additionally, self-described NS who meet criteria for any sleep disorder and those insomnia sufferers who meet criteria for a comorbid sleep disorder in addition to PI will also be excluded.

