## Power Considerations:

We conducted power calculations for the study proposed using data from our previous two studies that compared reaction time performances of PI and NS participants. From the archival data sets used for these studies we obtained estimates of mean response latencies (reaction times) correct response rates and error rates for PI and NS groups to estimate the sample size needed to test the 2 study hypotheses. All power calculations were conducted using the proc power procedures available in SAS, version 9.2.

Hypothesis 1 entails testing the simple main effect of group membership (PI vs. NS) on neuro-cognitive performance. As a proxy for global performances we used response latency, correct response rate and error rate data derived from our 2008 study and our above referenced pilot study. Those studies showed the following information in comparisons of our hyperaroused PI group and normally alert NS group.

Measure	PI group	NS group	Sample standard deviation
Mean response latency - msec	470.6	420.8	112.1
Mean # correct responses	75.7	77.5	3.74
Means # errors	4.46	2.60	3.45

Given these data and assuming  $\alpha = .05$ , and 82 subjects in each of these two groups we would have a .93 power to detect the predicted group differences in their mean error rates across trials, .87 power to detect the predicted differences in mean correct response rates, and .81 power to detect the predicted differences in mean reaction time latencies.

Hypothesis 2 entails testing the interaction term showing that difficult reaction time tasks will show significant differences between PI and NS whereas simple tests will not. Basically this analysis ultimately will entail a posteriori contrasts that show PI vs. NS group differences on complex tasks but not simple tasks. Again we used response latency data obtained from our 2008 study for conducting power analyses for this hypothesis. Those data showed the following mean group differences and group standard deviations for complex and simple tasks.

Measure	PI group	NS group	Sample standard deviation
Complex test response latency - msec	496.65	438.14	133.4
Simple test response latency - msec	247.9	226.4	66.8

Given these data and assuming  $\alpha = .05$ , and 82 subjects in each of these two groups we would have a .80 power to detect the predicted group differences on complex tasks but only .54 power to detect group differences on the simple tasks.

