On the basis of these calculations we will plan to enroll 82 hyperaroused PI sufferers and 82 NS in this study.

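### Loss of significance after adjusting for the Hyperarousal Scale score cannot confirm a role for hyperarousal, because the entry criteria give the two groups non-overlapping scores

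*Combined protocol and SAP*

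**What the plan says.** Study Design/Clinical Plan sets entry limits on the Hyperarousal Scale. Insomnia (PI) participants must "score $\geq 29$ on the Hyperarousal Scale"; normal sleepers (NS) must "score $< 25$ on the Hyperarousal Scale".

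Statistical Plans then uses the same score as a covariate. After the group main effect is tested for Hypothesis 1, the analysis is repeated with the score added, and the plan states: "Elimination of these statistical differences in repeat analyses that use hyperarousal scale scores as a covariate will confirm the role of hyperarousal". For Hypothesis 2 the wording is parallel: elimination of the differences with each participant's "score as a covariate will confirm the role of hyperarousal in explaining the observed group differences on complex tasks".

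The only other planned use of the score, at the end of Statistical Plans, relates it to the PSG and EEG measures. Nowhere is it related to performance within a group. There is no mediation test, no collinearity check and no caveat about the lack of overlap.

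**The concern.** Group is a deterministic function of the covariate: anyone at 29 or above is PI and anyone below 25 is NS. Three things follow.

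- Group and score are strongly correlated by design, so adding the score inflates the standard error of the group effect. The group term can lose significance without the score explaining anything.
- The adjusted group effect compares the groups at a common score, although no score is shared. It depends on extending a straight line across the empty interval from 25 to just under 29.
- No low-scoring PI and no high-scoring NS participants are enrolled, so the data hold no direct contrast between insomnia and hyperarousal.

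The rule also rewards imprecision: the weaker the adjusted test, the more likely the study is to declare hyperarousal's role confirmed. Background and Rationale gives further confirmation of hyperarousal's harmful effect as the first purpose of the project, and suggests that treatment needs may differ by arousal level. This covariate step is the only planned analysis that would attribute the performance deficit to the hyperarousal score.

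**Working it through.** **Inputs from Power Considerations** (82 per group, alpha .05):

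- Reaction time: (470.6 − 420.8)/112.1 gives d = .444
- Correct responses: (77.5 − 75.7)/3.74 gives d = .481
- Errors: (4.46 − 2.60)/3.45 gives d = .539
- Complex-task reaction time: (496.65 − 438.14)/133.4 gives d = .439

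**Step 1: reproduce the stated power.** Unadjusted power is approximately Φ(d√(n/2) − 1.96), with √(82/2) = 6.403.

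- Reaction time: .444 × 6.403 = 2.84; power .81 (stated .81)
- Correct responses: .481 × 6.403 = 3.08; power .87 (stated .87)
- Errors: .539 × 6.403 = 3.45; power .93 (stated .93)

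All three reproduce with a two-sided test. They describe the unadjusted comparison only.

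**Step 2: effect of adding the score.** With equal groups, let D be the gap between group mean scores and s the within-group SD. The variance inflation factor for the group term is VIF = 1/(1 − r²) = 1 + D²/(4s²). If the score has no within-group relation to performance, the adjusted group estimate is unbiased but its standard error is multiplied by √VIF.

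Worked case, reaction time, VIF 5.5: √5.5 = 2.35; 2.84/2.35 = 1.21; power is Φ(1.21 − 1.96), or about .23. The share of significant differences that become non-significant is then at least 1 − .23/.81 = 72%.

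Over an analytic range of D and s (VIF 2.4 to 7.3), adjusted power is .18 to .44 for reaction time, .21 to .50 for correct responses and .25 to .59 for errors.

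**Step 3: simulation under the rule's own null.** The group effect is as planned, and the score is independent of performance given group. Each simulated trial is tested by least squares with and without the score. The score distributions are assumptions; the non-overlap is the plan's.

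| Assumed scores | VIF | Reaction time: significance lost | Errors: significance lost |
|---|---|---|---|
| Truncated normal, PI about 36, NS about 18, SD 6 | 5.5 | 73% | 66% |
| Wider separation | 6.9 | 78% | not run |
| Six other truncated-normal or uniform shapes | 4.5–6.6 | 68–78% | 61–72% |
| Exponential tails from the cut-offs, scale 7 | 2.9 | 54% | 43% |
| Exponential tails from the cut-offs, most people near the gap | 2.6 | 50% | 41% |
| Exponential tails so wide that the gap is negligible | 2.05 | 40% | 30% |

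Percentages are of trials significant before adjustment. For correct responses, the six other shapes gave 66–74%. The last row is deliberately favourable to the plan. It agrees with the formula: two exponential tails running in opposite directions from the same point have D = 2s, so VIF = 1 + 1 = 2.

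**Step 4: what the same model says about the score.** Among these false confirmations, the score's own slope was non-significant in 91–97%. The rule would announce a role for hyperarousal while the same fitted model shows no detectable association between score and performance.

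**The case against.** The strongest reply is that neither hypothesis is a mediation claim. Hypothesis 1 is tested by the group main effect and Hypothesis 2 by the group-by-difficulty interaction with follow-up contrasts. The covariate step is a repeat analysis that leaves those tests and the sample size untouched. That is correct, and it limits the problem to the explanatory conclusion. It does not rescue that conclusion, which the plan states for both hypotheses.

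Other points also stand in part:

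- **Per-outcome rates.** The plan speaks of differences in the plural. If every one must vanish, the rate is lower. With three outcomes at the plan's effect sizes and assumed inter-outcome correlations of 0 to .6, all three were lost, given that all three were significant, in 36–48% (truncated normal), 47–58% (wider separation) and 13–24% (exponential tails). The MANOVA step was not modelled. These rates are still too high for a rule said to confirm anything, and the plan does not state which reading applies.
- **Unknown distributions.** The size of the loss depends on within-group spread, which the documents do not give. It is not above half in every case.
- **Hypothesis 2.** The result carries over to the complex-task contrast, where d is .439 and adjusted power is .18 to .43 over the same VIF range. It has not been shown for the interaction: whether a between-subject covariate alters that term depends on including a score-by-difficulty term, which the plan does not specify.
- **The model already contains the useful estimate.** In a model with group and score, the score coefficient is the pooled within-group slope. Centring the score within group leaves that slope and its standard error unchanged. The fault lies in which coefficient is interpreted.

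**Conclusion.** The concern holds, and the rule is wrong as written. Followed exactly, it would often report that hyperarousal's role is confirmed when the score has no effect on performance. Per outcome this happens in roughly 40 to 80% of significant differences under plausible score distributions, and in 30 to 40% under the most favourable one tried. The exact rate rests on assumed distributions. The cause, disjoint scores used as a covariate for group, is fixed by the eligibility criteria. The mechanism is loss of precision, with no bias toward zero in this scenario, so a confidence interval for the adjusted difference would expose it and a significance rule conceals it. The stated power and the unadjusted PI–NS comparisons are not in question. The correction is essential for any claim that hyperarousal explains the deficit.

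**What to change.** 1. Delete both statements that elimination of the differences will confirm hyperarousal's role.
2. Fit group plus the group-mean-centred Hyperarousal Scale score, or separate PI and NS models. Report the within-group slope of each performance measure on the score with its 95% CI. Claim a role for hyperarousal only if that slope supports it, never because the group term loses significance.
3. If the score-adjusted group difference is still reported, give its CI and the VIF, and say that it relies on extrapolation between non-overlapping ranges.
4. State that the PI–NS contrast cannot separate insomnia from hyperarousal in this design.
5. Optionally, repeat step 2 with mean MSLT latency. Everyone has it and it is not itself an entry criterion, although the Epworth and napping criteria may narrow its range among PI participants.

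The cost is SAP wording and one re-expressed model, with no new data. The drawback is that restricted score ranges within groups will make the slopes imprecise and the conclusion more modest.
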